### 9.7.2 Primary Efficacy Outcome

Although this pilot study will not be powered to prove or disprove any

hypotheses regarding efficacy, preliminary data will be gathered to guide planning on a future full-scale trial in which the primary efficacy outcome will be change in the average frequency of urinary incontinence based on a validated 3-day symptom diary. To that end, frequency of incontinence will be assessed based on voiding diaries completed at screening/baseline, 8 weeks, and 12 weeks, as well as 12 weeks after the completion of the yoga therapy or physical conditioning programs. The total number of any, stress-type, and urgency-type incontinence episodes will be calculated for each diary and then divided by the total number of days of recording to calculate the average number of incontinence episodes per day of each type.

#### **9.7.3 Secondary Efficacy Outcomes**

Preliminary data will also be gathered to guide planning for a future full-scale trial evaluating secondary efficacy outcomes such as change in other symptom and quality-of-life outcomes associated with incontinence. To that end, changes in anxiety and perceived stress symptoms and incontinence-related quality of life will be assessed using validated questionnaires completed at screening/baseline, 8 weeks, and 12 weeks, as well as 12 weeks after the completion of yoga therapy or physical conditioning programs.

### **9.8 Data Analyses**

To address aim 1 (feasibility), descriptive statistical techniques will be used to describe rates of recruitment, randomization, retention, and adherence for each recruitment wave. If drop-out is substantial, we will conduct exploratory pooled logistic regression analyses to try to identify participant characteristics associated with drop-out. Similarly, if adherence is less than expected, we will use linear, logistic, and/or proportional odds models, depending on the distribution of the outcome, to explore associations of participant characteristics with levels of adherence both to classes and home practice.

To address aim 2 (preliminary efficacy for change in incontinence frequency), we will use linear mixed models with unstructured residual covariance matrix to conduct a preliminary analysis of the 8, 12, and 24 week changes from baseline in incontinence frequency, adjusting for the baseline values, and treating week as categorical. This will provide estimates of the residual standard deviation, intra-class correlation, and fitted between-group differences at each follow-up time point. To assess trends and persistence, we will compare estimated between-group differences across weeks. All estimates will be presented with 95% confidence intervals.

The methods specified for aim 2 will also be used for aim 3 (preliminary efficacy for secondary symptom and quality-of-life outcomes). Outcomes will be normalized as necessary before analysis, and checked for equal variance across group and visit. In previous studies, changes in incontinence frequency and in other symptom and quality-of-life scores have been approximately normally distributed.

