#### **4.1 Inclusion Criteria**

Candidates must meet all of the following criteria to participate in the study:

- Women aged 50 years or older who report urinary incontinence starting at least 3 months prior to screening
- Self-report at least 3 urinary incontinence episodes on a screening 3-day voiding diary (i.e., an average of at least one episode per day)
- Self-report urgency-predominant (i.e., at least half of incontinence episodes being urgency-type), stress-predominant (i.e., at least half of episodes being stress-type), or mixed-type (i.e., an equal number of stress- and urgency-type episodes) incontinence on the screening voiding diary
- Willing to refrain from initiating medical treatments that may affect their incontinence or voiding pattern during the study intervention period

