#### **6.2.4 Randomization and Blinding**

##### Randomization

Women who are confirmed to be eligible and available to take part in upcoming yoga or physical conditioning group class series will be randomized in a 1:1 ratio to one of the two intervention groups. Randomization will ideally take place within 1 month of completion of screening procedures, and in no cases will be able to take place more than 2 months after completion of screening procedures. Randomization must also take place within 2 weeks of the start of yoga or physical conditioning class series. If the Baseline Clinic Visit occurs within 2 weeks of the start of the yoga therapy or physical conditioning program, eligible participants will be randomized to one of the two interventions directly at this visit. If the Baseline Clinic Visit occurs more than 2 weeks before the start of the intervention program, eligible participants will be scheduled for a Randomization Telephone Call within two weeks of the start of the program to determine their intervention assignment.

During the Baseline Clinic visit or during the Randomization Telephone Call

(whichever is appropriate), randomization will be performed according to a pre-established computer-algorithm using randomly permuted blocks of sizes 2 and 4 (limited block size to ensure that the number of randomized participants within each strata always exceeds the block size).

Randomization will be stratified by clinical type of incontinence (i.e., stress, urgency, or mixed) to ensure adequacy of randomization among women with each major incontinence type. Randomization will be implemented. Prior to randomization, the research coordinator will complete a randomization checklist confirming that the participant meets all eligibility criteria.

Additionally, participants' availability and willingness to attend upcoming yoga or physical conditioning group classes will be re-confirmed before randomization assignment is obtained.

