Standard allocation concealment procedures will be followed to avoid manipulation of randomization. Prior to the start of recruitment, the randomization scheme will be developed by a statistical programmer who will have no contact with participants or role in data entry, cleaning, or analysis. To execute the randomization scheme, a research assistant who will also have no contact with participants or access to study data will then prepare a series of sealed, opaque envelopes containing group assignment, numbered consecutively with the randomization sequence numbers. When the participant is ready for randomization, study coordinators will enter the date, participant name, and study ID in the randomization log and select the next numbered envelope corresponding to the participants' type of incontinence (stress-, urgency-, or mixed-type) to determine group assignment. Once a participant has been randomized, she cannot be re-assigned to a different intervention group. All randomization envelopes will be retained for review; randomization dates and times should follow the order of the sequence numbers, providing a check on validity.

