## **9.2 Sample Size and Randomization**

The investigative team plans to randomize and monitor up to 90 participants, with approximately 45 randomized to the yoga therapy group and 45 to the physical conditioning control group. No formal sample size estimates or power analyses have been performed for this pilot study, as one of the goals of this pilot is to collect preliminary data that may be used to guide sample size estimates for a larger clinical trial, if indicated. Study data on the standard deviation, intra-class correlation, and between-group difference in change in incontinence frequency and other efficacy outcomes will be used to guide sample size projections for a future full-scale trial powered to detect a 25% greater reduction in incontinence frequency associated with yoga therapy.

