## 9.7 Outcomes

### 9.7.1 Feasibility Outcomes

The feasibility of recruiting and randomizing middle-aged and older women with urinary incontinence into a randomized trial of yoga therapy versus physical conditioning will be examined by calculating the average number of participants recruited and randomized per month and per recruitment wave. It is assumed that the study team will need to recruit and randomize 15 to 30 women in each 3-month enrollment wave to confirm ability to assemble a class size of 8 to 15 women per group per wave in a future full-scale trial.

The feasibility of retaining participants in this trial design will be assessed by monitoring rates of drop-out or loss-to-follow-up over 8 and 12 weeks of treatment as well as during the 12-week post-treatment follow-up period. Drop-out rates in both treatment groups are expected to increase over time (i.e., to be greater at 12 weeks than at 8 weeks), but remain less than 20% after 12 weeks of treatment and less than 30% at 12 weeks of post-treatment follow-up.

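### Randomisation is stratified by incontinence type, but the section 9.8 model leaves that factor out; adding it is a minor, nearly costless improvement

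*Combined protocol and SAP*

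**What the plan says.** Section 6.2.4 states: "Randomization will be stratified by clinical type of incontinence (i.e., stress, urgency, or mixed"). Sections 4.3 and 9.3 repeat this, with permuted blocks of 2 and 4. Under 6.2.4 the coordinators "will enter the date, participant name, and study ID in the randomization log and select the next numbered envelope corresponding to" the woman's type of incontinence, so each type has its own allocation sequence.

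Section 9.8 fits a linear mixed model with unstructured residual covariance to the 8-, 12- and 24-week changes, "adjusting for the baseline values, and treating week as categorical". Its outputs are the residual SD, the intra-class correlation and the between-group differences, with 95% intervals. For the secondary outcomes, "The methods specified for aim 2 will also be used for aim 3". Incontinence type appears in no analysis text. Section 9.2 says that the variance and effect estimates "will be used to guide sample size projections for a future full-scale trial".

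Section 6.1.5 lets covariate data guide adjustment, but only if the groups turn out unbalanced. Section 4.1 defines the two predominant types by a share of one half or more and the mixed type by equality: "at least half of episodes being stress-type), or mixed-type (i.e., an equal number of stress- and urgency-type episodes").

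**The concern.** Stratified allocation balances type between the arms, which removes most of its contribution to the sampling error of the treatment difference. A model without type leaves that contribution in the residual variance. If type is prognostic beyond the baseline value, the model-based standard error is then larger than the design warrants, leaving class effects aside, and the reported residual SD is larger than a type-adjusted future trial would face.

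The stake is limited: the width of the preliminary intervals, and one planning quantity that this pilot exists to supply. The adjustment allowed in section 6.1.5 does not fill the gap, because a factor balanced by design is unlikely to trigger it.

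**Working it through.** **No plan figure to reproduce.** Section 9.2 says that no sample size or power calculation was made, and no document gives the share of variance explained by type. That share, R², is assumed at 5%, 10% and 20% of the baseline-adjusted residual variance. With two equal main strata the stress-urgency gap is 2√R² = 0.45, 0.63 and 0.89 residual SD, so the last case is large.

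**Formula.** Omitting a balanced factor multiplies the residual SD and the interval width by about 1/√(1−R²), and the implied future sample size by 1/(1−R²) = 1.053, 1.111 and 1.250.

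**Planned model, simulated (2,000 replicates per case).**
- From the documents: 90 women, 1:1, blocks of 2 and 4 within type, visits at weeks 8, 12 and 24, unstructured covariance. Drop-out is set at the section 9.7.1 limits, which expect it to "remain less than 20% after 12 weeks of treatment and less than 30% at 12 weeks of post-treatment follow-up".
- Assumed: type mix 45/45/10%, between-visit correlation 0.6, 10% drop-out by week 8, drop-out at random, no treatment effect, no class clustering.
- Both models include arm and baseline by week; the second adds type by week.

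Results at 12 weeks, residual variance 1 (percentages may differ in the last digit from the ratio of the rounded columns):

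| R² | 1/√(1−R²) | CI half-width, without / with type | CI wider without type | Residual SD, without / with type | SD larger without type |
|---|---|---|---|---|---|
| 0 | 1.000 | 0.463 / 0.464 | −0.4% | – | – |
| 0.05 | 1.026 | 0.462 / 0.453 | 1.9% | 0.993 / 0.969 | 2.5% |
| 0.10 | 1.054 | 0.464 / 0.442 | 5.0% | 0.998 / 0.944 | 5.8% |
| 0.20 | 1.118 | 0.464 / 0.419 | 10.8% | 0.998 / 0.892 | 11.9% |

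The mean estimate was within 0.009 of zero at every week, so there is no bias. A separate single-visit simulation (6,000 runs, assumed mix 50/35/15%, 20% drop-out) gave width ratios of 1.023, 1.050 and 1.115, so the result depends little on the mix or the repeated-measures structure.

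**Cost if type predicts nothing.** Adding type widened the interval by 0.2%, 0.4% and 0.6% at weeks 8, 12 and 24. At a single visit with only 2% to 5% of women in the mixed stratum, the cost was 0.5% to 0.6%.

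**Comparison with the SD's sampling error.** With 20% drop-out, 90 × 0.8 = 72 women complete. With three fixed effects there are 69 degrees of freedom. The 95% range of √(df/χ²) is 0.857 to 1.200, or 0.735 to 1.440 when squared to the sample-size scale. The assumed inflation in N, about 5% to 25%, lies inside that range.

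**Class clustering.** A single-visit simulation (10,000 replicates) assumed five classes per arm of about nine women and a class ICC of 0.02; the documents fix neither. With class ignored in both models, coverage at R² = 0.05, 0.10 and 0.20 was 93.7%, 94.4% and 95.2% without type, and 93.2%, 93.3% and 93.0% with it.

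**The case against.** The strongest case for leaving the model alone is that this is an unpowered pilot with a preliminary analysis, the estimate is unbiased, and the effect on the SD is smaller than its sampling error. An SD that is somewhat too large also errs towards a larger future trial, and the point lapses if that trial does not adjust for type. No passage shows that type is prognostic beyond baseline, least of all for the anxiety, stress and depression scores. All of this stands, and it limits the point to a minor one. It does not argue for omission, since the most that adjustment loses is a few tenths of a percent of interval width.

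It can also be said that, with class effects ignored, the wider interval happens to compensate in part, and that adding type lowers coverage. The figures above show this. But two errors that offset each other by chance do not make a reason for omitting the stratum; clustering needs its own treatment.

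Two stronger readings are tempting. A reader might infer that the planned intervals are over-conservative on balance. The documents do not support this: sections 5.1 and 5.2 deliver both programmes in classes, and even a small class ICC removes the excess. A reader might also infer, from the three log items in section 6.2.4, that the stratum will be lost to the analyst. That does not hold either: 6.2.4 keeps all the numbered, type-specific envelopes, and sections 6.1.1, 9.7.2 and 10.1 have stress and urgency counts abstracted from the baseline diary.

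The overlap in section 4.1 is real as worded, because an equal split also satisfies both half-or-more definitions. It is small, because the same criterion expressly labels equal splits as mixed.

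**Conclusion.** The point holds as a minor, nearly costless improvement. The analysis model omits the factor that the randomisation balances. Validity is unaffected and no pilot conclusion changes. The stated sizes rest wholly on the assumed variance shares for type and on the simulation settings above; at the 5% share the effect is close to negligible, and the 20% share implies a large difference between stress and urgency. The effect on future sample size applies only if the future trial adjusts for type. Nothing here shows that the planned intervals over-cover, and nothing shows that the stratum cannot be recovered.

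**What to change.** In section 9.8, add the randomisation stratum (stress, urgency, mixed) as a fixed covariate in the aim 2 and aim 3 models. Code it as the stratum of the envelope drawn, carry it into the analysis dataset, and report the residual SD from that model. Type-by-week and baseline-by-week terms are optional; the simulated figures include both. No fixed rule for merging a small mixed stratum is needed.

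In section 4.1, reword the type definitions so that they exclude one another and an equal stress/urgency split falls only in the mixed stratum.

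The cost is a sentence in 9.8, one stratum variable and a one-line clarification. Statistically it is two degrees of freedom (two per visit if type-by-week is used), or about 0.5% of interval width if type is not prognostic. Class clustering has to be dealt with separately.

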## 10. DATA COLLECTION AND QUALITY ASSURANCE

### 10.1 Data Collection Forms

Study data will be obtained from participant-completed symptom diaries and logs, participant- or interviewer-administered questionnaires, physical examination and performance measures, and urine sampling/testing. Forms for recording or abstracting data will be developed specifically for this study, including:

- Voiding diary abstraction form: After participants complete their 3-day voiding diary at home, they will return the completed diary to the study clinic, and diary data will be abstracted using a Voiding Diary Abstraction Form. At the Baseline Visit, a clinical coordinator will abstract diary data for eligibility assessment purposes; at all post-randomization follow-up assessments, an analyst who is blinded to intervention assignment will abstract diary data.
- Questionnaires assessing anxiety and perceived stress, condition-specific quality of life, and participant satisfaction: These questionnaire forms will be completed by the participant during clinic visits and returned in person to a clinical coordinator, or completed by the participant at home and then mailed back to the study clinic (in the case of the 12 week post-treatment assessment). Questionnaire data collected after randomization will be entered into the electronic database by an analyst who is blinded to intervention assignment.
- Questionnaires assessing demographic history, general medical and urologic/urogynecologic history, medication use, tobacco and alcohol use, and physical activity and function: These questionnaires will be administered by a clinical coordinator during in-person study visits, and data from questionnaires will subsequently be entered by the coordinator into the electronic database. Because these data will not be used to assess efficacy outcomes, the coordinators who administer and enter data from these forms will not necessarily be blinded to intervention assignment.
- Physical examination, physical performance testing, and urine testing data forms: Clinical coordinators will record the results of height and weight measurements, blood pressure and heart rate measurements, physical performance testing, and urine dipstick and pregnancy testing on study-specific forms, and data from these forms will then be entered by coordinators into the electronic database. Because these data will not be used to assess any efficacy outcomes, the coordinators who are responsible for collecting, recording, and entering these data will not necessarily be blinded to intervention assignment.

### 10.2 Data Management

Data will be entered, managed, and edited using Research Electronic Data Capture (REDCap), a secure, web-based application developed by a multi-institutional consortium initiated at Vanderbilt University to support data capture for research studies. Data can be entered from any location with secure web authentication, data logging, and Secure Sockets Layer (SSL) encryption. REDCap offers advanced features including auto-validation, branching logic, stop actions, data import functions, and data comparison functions. The REDCap system complies with HIPAA regulations, data will be stored on HIPAA compliant servers, protected by firewalls.

## **10.3 Quality Assurance**

### **10.3.1 Staff Training**

All investigators, project directors, and clinical coordinators involved in the study will complete training in Human Subjects Research offered by the Collaborative Institutional Training Initiative (CITI), which includes specific training modules on assessing risk to subjects, avoiding group harms, conflicts of interest, cultural competence, FDA-regulated research, HIPAA-regulated research, informed consent, IRB member responsibilities, IRB chair responsibilities, records-based research, research with vulnerable subjects, and unanticipated problems and reporting. All investigators, project directors, and coordinators will maintain active CITI certification for the duration of the study.

Coordinators and analysts involved in data collection will also attend a study-specific training meeting led by the principal investigator and the project directors prior to the start of participant recruitment. At a minimum, the training meeting will include: (1) an introduction to the goals, design, and procedures of the LILA study; (2) an overview of goals, structure, and procedures for administering and abstracting data from the voiding diary and other study-specific data collection measures; (3) a review of definitions and procedures for assessing, documenting, and reporting adverse events.

Coordinators and analysts will also receive training and undergo supervised practice in reviewing and abstracting data from the voiding diary as the primary efficacy measure in the trial. They will also receive training and undergo supervised practice performing measurements of blood pressure and heart rate and assessing physical function/performance measures. Following the training, clinical staff will be certified for performing these functions.

### **10.3.2 Data Quality Assessment**

Data collection forms will be reviewed on an ongoing basis for data completeness and accuracy as well as protocol compliance. All forms used to collect data on primary and secondary efficacy outcomes (i.e., voiding diary abstraction forms, questionnaires addressing anxiety and perceived stress and condition-specific quality of life) will be verified against paper-based source forms by a staff member who was not involved in entering the data.

Quality of data entry will be periodically assessed using measures such as number of missing forms, number of missing queries, and proportion of all study variables queried. The results of assessment of data quality will be incorporated into study progress reports for scheduled DSM meetings.

### **10.3.3 Protocol Deviations**

Exceptions to the protocol are expected to occur rarely or not at all and, where possible, will be approved in advance by the principal investigator. Protocol exceptions may occur for the following reasons:

- exceptions necessary to protect the safety or well-being of a participant (in this case, the protocol exception should apply to that participant only)

- exceptions due to oversight or error on the part of study staff, which are subsequently detected by the investigators, project managers, clinical coordinators, or data analysts.

For each protocol exception, study staff will document the exception on a Protocol Exceptions Log (located in the Regulatory Binder). Entries in the Protocol Exceptions Log should include the participant ID, date of the exception, date exception is being recorded, description of exception, and action taken in response to the exception, if any. The principal investigator will document approval for each exception determined in advance, or acknowledgement for each exception detected after the fact.

For this study, missed yoga therapy or physical conditioning classes will not be considered a protocol deviation, and neither will failure to complete recommended home practice sessions, although study staff will make every effort to promote adherence to classes and home practice (see section 5.4).

